7. PATIENT SELECTION: ELIGIBILITY

7.1. Inclusion Criteria

1. Hepatocellular carcinoma, diagnosed either by biopsy or by combination of cirrhosis and imaging criteria (contrast-enhanced CT or MRI).
2. Tumor confined to liver with no vascular invasion and no evidence of extrahepatic disease.
3. Patient evaluated by institutional Liver Transplant team and deemed eligible for transplant.
4. At least 1 lesion, not previously irradiated, that qualifies as a RECIST 1.1 target lesion (TL) at baseline. Tumor assessment by computed tomography (CT) scan or magnetic resonance imaging (MRI) must be performed within 28 days prior to randomization.
5. No prior therapy for HCC at any time.
6. Age ≥18 years at the time of study entry.
7. ECOG score of 0 or 1

8. Child-Pugh Score of 5, 6, or 7
9. Body weight >30 kg
10. Patients must have adequate organ and marrow function as defined below:

Hemoglobin	≥9.0 g/dL
Absolute neutrophil count	≥1.0 × 10 ⁹ /L
Platelet count	≥50 × 10 ⁹ /L
Serum bilirubin*	≤3 mg/dL
AST(SGOT)/ALT(SGPT)	≤2.5 x institutional upper limit of normal unless liver metastases are present, in which case it must be ≤5x ULN
Creatinine	< 1.5 ULN
Measured creatinine clearance	>40 mL/min
OR	
Calculated creatinine clearance (CL)	
CL>40 mL/min by the Cockcroft-Gault formula (Cockcroft and Gault 1976) or by 24-hour urine collection for determination of creatinine clearance:
 
Males: Creatinine CL = $\frac{\text{Weight (kg)} \times (140 - \text{Age})}{72 \times \text{serum creatinine (mg/dL)}}$ (mL/min)
 
Females: Creatinine CL = $\frac{\text{Weight (kg)} \times (140 - \text{Age})}{72 \times \text{serum creatinine (mg/dL)}} \times 0.85$ (mL/min)

11. Capable of giving signed informed consent which includes compliance with the requirements and restrictions listed in the informed consent form (ICF) and in this protocol.
12. Patient is willing and able to comply with the protocol for the duration of the study including undergoing treatment and scheduled visits and examinations including follow up.

7.2. Exclusion Criteria

1. Extrahepatic disease.
2. Variceal bleeding during 3 months prior to registration.
3. Any autoimmune disease deemed a risk in the setting of immunotherapy per treating physician's judgment, such as PSC, PBC, autoimmune hepatitis, etc.
4. Any other illness or patient condition deemed a medical or logistical barrier for protocol therapy per treating physician's judgment.

5. Concurrent enrollment in another clinical study, unless it is an observational (non-interventional) clinical study or during the follow-up period of an interventional study
6. Participation in another clinical study with an investigational product during the last 12 months Patients who have received other investigational agents previously who are no longer receiving these investigational agents may be eligible at the discretion of the PI.
7. Major surgical procedure (as defined by the Investigator) within 28 days prior to the first dose of IP. Note: Local surgery of isolated lesions for palliative intent is acceptable.
8. History of allogenic organ transplantation.
9. History of another primary malignancy except for:
 - a. Malignancy treated with curative intent and with no known active disease ≥ 5 years before the first dose of IP and of low potential risk for recurrence
 - b. Adequately treated non-melanoma skin cancer or lentigo maligna without evidence of disease
 - c. Adequately treated carcinoma in situ without evidence of disease
10. Active or prior documented autoimmune or inflammatory disorders (including inflammatory bowel disease [e.g., colitis or Crohn's disease], diverticulitis [with the exception of diverticulosis], systemic lupus erythematosus, Sarcoidosis syndrome, or Wegener syndrome [granulomatosis with polyangiitis, Graves' disease, rheumatoid arthritis, hypophysitis, uveitis, etc.]). The following are exceptions to this criterion:
 - a. Patients with vitiligo or alopecia
 - b. Patients with hypothyroidism (e.g., following Hashimoto syndrome) stable on hormone replacement
 - c. Any chronic skin condition that does not require systemic therapy
 - d. Patients without active disease in the last 5 years may be included but only after consultation with the study physician
 - e. Patients with celiac disease controlled by diet alone
11. Uncontrolled intercurrent illness, including but not limited to, ongoing or active infection, symptomatic congestive heart failure, uncontrolled hypertension, unstable angina pectoris, cardiac arrhythmia, interstitial lung disease, serious chronic gastrointestinal conditions associated with diarrhea, or psychiatric illness/social situations that would limit compliance with study requirement, substantially increase risk of incurring AEs or compromise the ability of the patient to give written informed consent
12. History of leptomeningeal carcinomatosis
13. History of active primary immunodeficiency
14. Active infection including tuberculosis (clinical evaluation that includes clinical history, physical examination and radiographic findings, and TB testing in line with local practice), hepatitis B (known positive HBV surface antigen (HBsAg) result), hepatitis C, Patients with a past or resolved HBV infection (defined as the presence of hepatitis B

core antibody [anti-HBc] and absence of HBsAg) are eligible. Patients positive for hepatitis C (HCV) antibody are eligible only if polymerase chain reaction is negative for HCV RNA.

15. Current or prior use of immunosuppressive medication within 14 days before the first dose of durvalumab or tremelimumab. The following are exceptions to this criterion:
 - a. Intranasal, inhaled, topical steroids, or local steroid injections (e.g., intra articular injection)
 - b. Systemic corticosteroids at physiologic doses not to exceed 10 mg/day of prednisone or its equivalent
 - c. Steroids as premedication for hypersensitivity reactions (e.g., CT scan premedication)
16. Receipt of live attenuated vaccine within 30 days prior to the first dose of IP. Note: Patients, if enrolled, should not receive live vaccine while receiving IP and up to 30 days after the last dose of IP.
17. Female patients who are pregnant or breastfeeding or male or female patients of reproductive potential who are not willing to employ effective birth control from screening to 180 days after the last dose of durvalumab + tremelimumab combination therapy.
18. Known allergy or hypersensitivity to any of the study drugs or any of the study drug excipients.
19. Prior randomization or treatment in a previous durvalumab and/or tremelimumab clinical study regardless of treatment arm assignment.
20. Judgment by the investigator that the patient is unsuitable to participate in the study and the patient is unlikely to comply with study procedures, restrictions and requirements.

7.3. Inclusion of Women and Minorities

Women and minorities will be included.

8. REGISTRATION PROCEDURES

8.1. Assignment of Screening and Subject Numbers

All consented subjects will be given a unique screening number that will be used to identify the subject for all procedures that occur prior to eligibility being confirmed. Each subject will be assigned only one screening number. Screening numbers must not be re-used for different subjects. The screening number will become the subject's study number once they are confirmed to be eligible (registered).

Patients who are a screen-failures may not typically be re-screened at a later time to determine if they could meet eligibility criteria unless the UC PI determines that re-screening may be appropriate; such as, when the screen-failure was due to a procedure being out of window rather than an indication that a patient's health may preclude meeting eligibility.

Any patient for whom the UC PI does give express permission for re-screening will be provided with a new screening number for each instance for which they are being re-screened. Results from assessments performed during the prior screening period are acceptable in lieu of a repeat screening test if performed within the protocol specified time frames.

8.2. Patient Screening

All subjects must provide informed consent prior to the initiation of study procedures, including screening. Results of a test performed prior to the subject signing consent as part of routine clinical management are acceptable in lieu of a screening test if performed within the specified time frame. Screening procedures are to be completed within 28 days prior to the first dose trial treatment except for the following:

- Laboratory tests and ECOG PS are to be performed within 10 days prior to the first dose of trial treatment.
- For women of reproductive potential, a serum pregnancy test will be performed within 7 days prior to the first dose of trial treatment. A urine test may be considered if serum test is not appropriate.

Subjects may be rescreened after initially failing to meet the inclusion/exclusion criteria as long as they have not yet started treatment; however, the cost of re-screening tests will not be covered by the study. Results from assessments performed during the initial screening period are acceptable in lieu of a repeat screening test if performed within the specified time frame and the inclusion/exclusion criteria is met.

8.3. Patient Registration

To determine if a patient meets eligibility criteria, the following documents should be compiled by research team and provided to the University of Cincinnati PI and UC Project Manager/Monitor as soon after the subject has consented as possible:

- Study informed consent form signed and dated by the patient.
- Source documents verifying every inclusion and exclusion criteria for the patient.

Upon receipt, the UC PI or qualified designee will confirm subject eligibility and the UC Project Manager/Monitor will perform a double check. Eligibility must be confirmed prior to the initiation of any study procedures. Once eligibility is confirmed, a research team member may then proceed to register the subject to enrolled status within the study EDC.

8.4. General Guidelines

Following registration, patients should begin protocol treatment within 28 days. Issues that would cause significant treatment delays should be discussed with the Principal Investigator.

9. BIOMARKER, CORRELATIVE, AND SPECIAL STUDIES

9.1. Biomarker Plan

List of Biomarker Assays in Order of Priority

Priority	Biomarker Name	Biomarker Assay	Biomarker Type and Purpose	M/O	Timing	Specimen	Quantity Needed	Lab
1	Peripheral blood immune phenotypes	Flow cytometry	Exploratory To determine changes in peripheral blood immune cell populations over the course of treatment, with a focus on CD3+ T cell populations	O	Baseline, post-immunotherapy, and post-transplant	Peripheral blood mononuclear cells isolated from whole blood	20mLs collected in EDTA tubes at each time-point	UCCC CTO Lab
2	Gut microbial composition	Metagenomic sequencing	Exploratory To evaluate differences in the gastrointestinal microbiome in patients that may act as biomarkers for response	O	Baseline	Stool sample collected via Omnigene stool collection kits	A small, dime sized amount of fecal matter as indicated by instructions in the Omnigene collection kit	[name], UC Biorepository, and Cincinnati Children's Hospital Medical Precision Metagenomics Laboratory

Specimen Collection Schedule

Specimen Type	Baseline (Pre-treatment but after Eligibility Confirmed)	Post- immunotherapy	Post- transplant
Peripheral blood, 20mLs in two 10mL EDTA tubes	X	X	X (4 weeks post-transplant +/- 3 days)
Stool sample	X		

9.2. Exploratory/Ancillary Correlative Studies

9.2.1. Peripheral blood immune phenotypes

Collection of Specimen(s): Two 10mL EDTA blood collection tubes (purple top) for a total of 20mLs of whole blood will be collected at:

- Baseline (after eligibility confirmation but prior to I/O)
- Post-Immunotherapy
- Post-transplant

Handling of Specimens(s): Standard operating procedures; Do not shake of freeze tube; label each blood collection tube with the following information:

- Clinical trial study number: UCCC-GI-21-01
- Subject's ID: GI-21-01-01
- Date and time of collection: (example 3/18/2021, 15:00)
- Study time-point (Baseline)

Shipping of Specimen(s): Samples from subsites will be shipped ambient day of collection according to standard operating procedures outlined in the laboratory manual. Specimens are to be shipped to the UCCC CTO Translational Laboratory at:

- [name]
- Sites must email study monitor and [contact] to provide notice of shipping and avoid shipping for arrival on Fridays and holidays as specified in lab manual.

Site(s) Performing Correlative Study:

- University of Cincinnati, UCCC CTO Laboratory ([contact]).

9.2.2. Gut microbial composition

Collection of Specimen(s): Patients will be provided with an Omnigene Stool Collection kit to take home for stool collection at the Baseline timepoint (after eligibility is confirmed, prior to I/O). Kit includes the following:

- Pre-paid return box
- Printed sample collection instructions
- Packaged sample collection kit
- Pre-printed sample label
- Biohazard bag
- 1 pair of latex-free exam gloves

Handling of Specimens(s): Specimens will be collected by the patient at home and handled according to SOPs provided with the collection kit.

Shipping of Specimen(s): Kits will be returned to the office of [name] and department study coordinator will coordinate delivery of kits to the UC Biorepository for sample processing.

Site(s) Performing Correlative Study: [name], University of Cincinnati, UC Biorepository, Cincinnati Children's Hospital Medical Precision Metagenomics Laboratory
Please consult the study laboratory manual for more details.

10. TREATMENT PLAN

The Study Calendar - Section 3 summarizes the trial procedures to be performed at each visit.

10.1. Agent Administration

Treatment will be administered on an outpatient basis. No investigational or commercial agents or therapies other than those described below may be administered with the intent to treat the patient's malignancy.

Regimen Description					
Agent	Premedications ; Precautions	Dose	Route	Schedule	Cycle Length
Durvalumab	None	1500 mg	IV	Q4W	4 weeks
Tremelimumab	None	300 mg	IV	1 dose on day 1 of only the first cycle	
The above for up to 4 months (5 doses durvalumab)					

10.2. Durvalumab + tremelimumab combination therapy

Tremelimumab 300 mg via IV infusion x 1 dose on day 1 of the first cycle, plus durvalumab 1500 mg via IV infusion Q4W starting on day 1, for up to a maximum of 4 months (5 doses of durvalumab). N.B If a patient's weight falls to 30kg or below (≤ 30 kg), then the patient should receive weight-based dosing equivalent to 20 mg/kg of durvalumab Q4W after consultation between the investigator and study physician, until the weight improves to above 30 kg (>30 kg), at which point the patient should start receiving the fixed dosing of durvalumab 1500 mg Q4W).

Patients will be treated with the immunotherapy combination for up to 4 months. After a minimum 28 day gap following the final durvalumab dose, they will undergo locoregional therapy per institutional standards. Eventually, after a minimum 72-day gap from the end of immunotherapy, they will undergo liver transplant.

Tremelimumab will be administered first over 1 hour; the durvalumab infusion will then be started approximately 1 hour after the end of the tremelimumab infusion to allow for a 1 hour observation

period. Standard infusion time for each is 1 hour, however if there are interruptions, the total allowed time must not exceed 4 hours from the start of infusion at room temperature per infusion.

10.3. General Concomitant Medication and Supportive Care Guidelines

The Principal Investigator must be informed as soon as possible about any medication taken from the time of screening until the end of the clinical phase of the study (final study visit). Any concomitant medication(s), including herbal preparations, taken during the study will be recorded in the EDC REDCap and on concomitant medication logs. Restricted, prohibited, and permitted concomitant medications are described in the following tables. There are no prohibited therapies during the Post-Treatment Follow-up Phase.

10.3.1. Permitted concomitant medications

Table 1. Supportive medications

Supportive medication/class of drug:	Usage:
Concomitant medications or treatments (e.g., acetaminophen or diphenhydramine) deemed necessary to provide adequate prophylactic or supportive care, except for those medications identified as “prohibited,” as listed in the table below.	To be administered as prescribed by the Investigator
Best supportive care (including antibiotics, nutritional support, correction of metabolic disorders, optimal symptom control, and pain management [including palliative radiotherapy to non-target lesions, etc.])	Should be used, when necessary, for all patients
Inactivated viruses, such as those in the influenza vaccine	Permitted

10.3.2. Excluded concomitant medications

Table 2 Prohibited concomitant medications

Prohibited medication/class of drug:	Usage:
Any investigational anticancer therapy other than those under investigation in this study	Should not be given concomitantly whilst the patient is on study treatment
mAbs against CTLA-4, PD-1, or PD-L1 other than those under investigation in this study	Should not be given concomitantly whilst the patient is on study treatment
Any concurrent chemotherapy, radiotherapy, immunotherapy, or biologic or hormonal therapy for cancer treatment other than those under investigation in this	Should not be given concomitantly whilst the patient is on study treatment. (Concurrent use of hormones for non-cancer-related conditions [e.g., insulin for diabetes and hormone replacement therapy] is

Prohibited medication/class of drug:	Usage:
study	acceptable. Local treatment of isolated lesions, excluding target lesions, for palliative intent is acceptable [e.g., by local surgery or radiotherapy])
Immunosuppressive medications including, but not limited to, systemic corticosteroids at doses exceeding 10 mg/day of prednisone or equivalent, methotrexate, azathioprine, and tumor necrosis factor- α blockers	
Should not be given concomitantly or used for premedication prior to the I-O infusions. The following are allowed exceptions:
 
 • Use of immunosuppressive medications for the management of IP-related AEs, • Use in patients with contrast allergies. • In addition, use of inhaled, topical, and intranasal corticosteroids is permitted. 
A temporary period of steroids will be allowed if clinically indicated and considered to be essential for the management of non-immunotherapy related events experienced by the patient (e.g., chronic obstructive pulmonary disease, radiation, nausea, etc.).

EGFR TKIs	
Should not be given concomitantly.
 
Should be used with caution in the 90 days post last dose of durvalumab.
 
Increased incidences of pneumonitis (with third generation EGFR TKIs) and increased incidence of transaminase increases (with 1st generation EGFR TKIs) has been reported when durvalumab has been given concomitantly.

Live attenuated vaccines	Should not be given through 30 days after the last dose of IP (including SoC)
Herbal and natural remedies which may have immune-modulating effects	Should not be given concomitantly unless agreed by the UC PI.

10.4. Interim Safety Analysis

During immunotherapy, grade 3-5 AEs will be monitored and at 10 patients enrolled an interim safety analysis will be performed. We will halt enrollment and assess safety in detail to determine if the study should continue, in discussion with AstraZeneca if:

- Of the first 10 patients, if ≥ 3 patients have to discontinue immunotherapy due to treatment related AEs and/or
- Of the first 10, if ≥ 3 patients experience SAEs related to locoregional therapy after immunotherapy and/or
- Of the first 10, if ≥ 3 patients fail to reach liver transplant due to immunotherapy toxicity and/or
- Of the first 10 patients, if ≥ 3 deaths are encountered, from enrollment to up to 30 days after transplant

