Study Design: ESR-20-21010 is a single-arm, open-label, Phase II, multicenter clinical trial designed to evaluate the safety and efficacy of durvalumab and tremelimumab for the treatment of hepatocellular carcinoma (HCC) patients who have cirrhosis or portal hypertension and are listed for a liver transplant. The key eligibility requirements include HCC, Child-Pugh score of up to 7, and ECOG PS of 0 or 1. Patients will be treated with the immunotherapy combination for up to 4 months. After a minimum 28 day gap following the final durvalumab dose, they will undergo locoregional therapy per institutional standards. Eventually, after a minimum 72-day gap from the end of immunotherapy, they will undergo liver transplant.

The primary endpoint is proportion of patients experiencing post-transplant rejection, graft loss, death, or loss to follow up (within 30 days of transplant). A total of 30 patients are to be enrolled, to allow at least 20 transplants for adequate primary endpoint analysis. An interim analysis after 10 patients will be performed to ensure safety. If there are untoward safety signals, study modification/discontinuation will be taken into consideration by the UCCC DSMB, investigators, the sponsor-investigator and AstraZeneca during the study and at interim analysis.

Number of Centers: 3

Number of Patients: 30

Study Population: HCC patients who have cirrhosis or portal hypertension and are listed for a liver transplant.

Inclusion Criteria:
 
 1. Hepatocellular carcinoma, diagnosed either by biopsy or by combination of cirrhosis and imaging criteria (contrast-enhanced CT or MRI) 2. Tumor confined to liver (no evidence of extrahepatic disease), with no macrovascular invasion 3. Patient evaluated by institutional Liver Transplant team and deemed eligible for transplant 4. Measurable disease by RECIST 1.1 5. No prior therapy for HCC 6. Adult patient (Age ≥ 18) 7. ECOG = 0 or 1 Child-Pugh Score = 5, 6, or 7 8. Creatinine < 1.5 ULN 9. Body weight > 30 kg

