10.5. Duration of Therapy

In the absence of treatment delays due to adverse event(s), treatment may continue for up to 4 months or until one of the following criteria applies:

- Clinical disease progression
- RECIST 1.1 and/or mRECIST defined radiological progression
- Intercurrent illness that prevents further administration of treatment
- Unacceptable adverse event(s)
- Patient decides to withdraw consent for the study treatment
- General or specific changes in the patient's condition render the patient unacceptable for further treatment in the judgment of the investigator
- Patient non-compliance
- Pregnancy
 - All women of child bearing potential should be instructed to contact the investigator immediately if they suspect they might be pregnant (*e.g.*, missed or late menstrual period) at any time during study participation.
- Termination of the study by University of Cincinnati PI
- The drug manufacturer can no longer provide the study agents

The reason(s) for protocol therapy discontinuation, the reason(s) for study removal, and the corresponding dates must be documented in the study EDC (REDCAP) and within study source documentation.

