14.2. Sample Size/Accrual Rate

A total of 30 patients are to be enrolled, to allow at least 20 transplants for adequate primary endpoint analysis.

During immunotherapy, grade 3-5 AEs will be monitored. In the pivotal study of durvalumab and tremelimumab (Kelley et al, Abstract 4508 at ASCO 2020), 16% had Tx related (TR) SAEs, and 11% had discontinuation of treatment due to TR AEs. We will use these guardrails for interim safety analyses at 10 patients. We will pause enrollment and assess safety in detail to determine if the study should continue, in discussion with AstraZeneca if:

- Of the first 10 patients, if ≥ 3 patients have to discontinue immunotherapy due to treatment related AEs and/or;
- Of the first 10, if ≥ 3 patients experience SAEs related to locoregional therapy after immunotherapy and/or;
- Of the first 10, if ≥ 3 patients fail to reach liver transplant due to immunotherapy toxicity and/or;
- Of the first 10 patients, if ≥ 3 deaths are encountered, from enrollment to up to 30 days after transplant.

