15.14. Reporting of SAEs & AEs to regulatory authorities

All SAEs have to be reported, whether or not considered causally related to the investigational product.

SAEs should be reported using a MedWatch form within 24 hours of becoming aware of the initial SAE or any follow-up information regarding the SAE. SAEs should be reported on MedWatch Form 3500A, which can be accessed at: <https://www.fda.gov/safety/medical-product-safety-information/medwatch-forms-fda-safety-reporting>

The study team will report SAEs to the UCCC DSMB, IRB of record and FDA according to their respective prompt reporting timeframes. Sub-sites must report SAEs determined to be attributable to the study interventions within 24 hours to the University of Cincinnati PI and study monitor.

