17.3. Data Safety Monitoring Board

Any new significant finding that may affect the patient's willingness to continue in the study will be shared with patients. Immediately after the study is approved and before the first patient is enrolled, investigators will meet, develop and finalize all measurements/variables for the study. Each patient, once enrolled, will be provided a unique ID for the study. Personal information, such as name, SSN, address, phone number and DOB, will be de-identified whenever possible from study records. Confidentiality will be maintained during the phases of the trial including preparation of interim results, review, and response to internal auditing or DSMB or IRB recommendations.

Exceptions may be made under circumstances where there are serious adverse events or when it is deemed appropriate for patient safety.

Study progress will be monitored regularly by the UCCC Data Safety Monitoring Board (DSMB). Membership consists of persons independent of, and without any conflicts of interest with, this trial. The DSMB includes experts in the fields of relevant clinical expertise (oncology) and biostatistics.

It is the responsibility of the UC Investigator to ensure that the DSMB is apprised of all new safety information relevant to the study. Study progress & safety information will be prepared by the DSMB Coordinator with input from the UC PI as to the current status of the trial. This compiled information presented to the DSMB will include: a narrative summary from the UC PI as to trial progress and identification of any trends of significance or explanation of any SAEs or other safety related events; the accrual rate with projected completion date for the accrual phase; exclusion rates and reasons when relevant; pretreatment characteristics of patients accrued when relevant; and, the frequency and severity of adverse events.

The DSMB will function in an advisory capacity and recommendations/requests from the DSMB will be reviewed by the UC investigator and promptly addressed.

The study data from participating sub-sites will be reviewed remotely via the study EDC REDCap and in person by the Study Monitor as per the study Monitoring Plan (Plan kept on file with UCCC CTO office).

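### The pause rule for toxicity discontinuations counts only the first 10 of 30 patients; a review trigger at 6 or more of the first 20 would extend it cheaply

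*Combined protocol and SAP*

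**What the plan says.** Section 10.4 sets the timing: "During immunotherapy, grade 3-5 AEs will be monitored and at 10 patients enrolled an interim safety analysis will be performed". Enrolment halts for a detailed safety assessment, in discussion with the drug manufacturer, if any of four counts reaches 3 among the first 10 patients. The first count is of those in whom "patients have to discontinue immunotherapy due to treatment related AEs". Section 14.2 repeats the four rules, says "We will use these guardrails for interim safety analyses at 10 patients", and gives the benchmark from the earlier study of the combination: "11% had discontinuation of treatment due to TR AEs". Planned enrolment is 30.

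Oversight outside these rules continues throughout. The synopsis says "study modification/discontinuation will be taken into consideration by the UCCC DSMB, investigators, the sponsor-investigator and AstraZeneca during the study and at interim analysis". Section 15.14 says "The study team will report SAEs to the UCCC DSMB, IRB of record and FDA according to their respective prompt reporting timeframes". Section 17.3 has the board monitor progress regularly and receive the frequency and severity of adverse events. On data capture, section 10.5 says "The reason(s) for protocol therapy discontinuation, the reason(s) for study removal, and the corresponding dates must be documented in the study EDC".

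**The concern.** A treatment-related discontinuation in patient 11 or later never counts towards a written limit. Read literally, 2 of the first 10 patients and all 20 later ones (22 of 30) could stop for toxicity without meeting the rule.

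The sponsor judged a numeric prompt useful for the first third of enrolment, but 10 patients say little about whether the rate exceeds 11%. If the rate is higher and the first 10 happen to look acceptable, the people reviewing the study have no agreed count that tells them to look again. The stake is limited, because crossing the limit leads to a review and review is possible at any time. What is missing is a common, pre-agreed point for it.

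**Working it through.** **Inputs.** Rule: at least 3 of the first 10 (sections 10.4 and 14.2). Benchmark: 11% (section 14.2). Second documented rate: 17% (section 15.4), which covers discontinuation for any adverse event at a lower tremelimumab dose. Rates of 22% (twice the benchmark) and 30% are assumptions; the plan names no unacceptable rate. Enrolment: 30 patients over four years (synopsis), or 30/48 = 0.625 per month if uniform. Treatment: up to five durvalumab doses at four-week intervals (section 10.2). The plan states no operating characteristics for the pause rule, so there is no figure of its own to reproduce.

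**Step 1: the rule as written.** With X₁₀ ~ Binomial(10, p), P(pause) = 1 − P(X₁₀ ≤ 2). P(X₁₀ ≤ 2) is 0.912, 0.766, 0.617 and 0.383 at p = 0.11, 0.17, 0.22 and 0.30.

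**Step 2: add a limit of r among the first 20.** The added chance of a pause is

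Σ over x = 0, 1, 2 of P(X₁₀ = x) × P(Binomial(10, p) ≥ r − x).

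For r = 6 and p = 0.30: 0.0282 × 0.0473 + 0.1211 × 0.1503 + 0.2335 × 0.3504 = 0.0013 + 0.0182 + 0.0818 = 0.1013. The total is 0.6172 + 0.1013, or 0.7186 before rounding of the terms. Because the count can only rise, checking after each patient or once at 20 gives the same probability.

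| True rate | ≥3/10 alone | with ≥6/20 | added | with ≥5/20 | added |
|---|---|---|---|---|---|
| 11% | 8.8% | 9.3% | 0.5 | 11.5% | 2.7 |
| 17% | 23.4% | 26.2% | 2.7 | 32.9% | 9.5 |
| 22% | 38.3% | 44.3% | 6.0 | 53.9% | 15.6 |
| 30% | 61.7% | 71.9% | 10.1 | 80.8% | 19.1 |

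Added chances are in percentage points.

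**Step 3: when added pauses occur.** The mean patient number at an added pause is 18.7, 18.5, 18.4 and 18.1 for ≥6/20, and 18.1, 17.9, 17.7 and 17.2 for ≥5/20, across the four rates.

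**Step 4: patients spared.** If a pause ended enrolment and events were seen at once, the expected number spared is Σ P(added pause at patient i) × (30 − i). At 17%, 22% and 30% this is 0.31, 0.69 and 1.20 for ≥6/20, and 1.15, 1.92 and 2.43 for ≥5/20.

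If every event were seen only at the fifth dose, the delay is 4 × 28 = 112 days, during which 0.625 × 112/30.44 = 2.3 more patients enrol. Subtracting 2.3 × the added pause probability leaves 0.25, 0.55 and 0.97 for ≥6/20, and 0.93, 1.56 and 1.99 for ≥5/20. All are upper bounds, because the pause does not bind.

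**Step 5: a rate that rises after patient 10.** If the rate is 11% in the first 10 patients and 30%, 40% or 50% in the next 10 (assumed), the chance that the first look passes and ≥6/20 then triggers is 14.8%, 32.6% or 53.5%. The written rule adds nothing in these cases.

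**The case against.** The strongest reply is that review already covers all 30 patients. The board, the investigators, the sponsor-investigator and the manufacturer may act at any time; serious events reach the board; and section 10.4 itself has grade 3–5 events monitored during immunotherapy. One early numeric look plus discretion is a legitimate design for a 30-patient single-arm pilot. This stands, and it is why the point is not a missing safeguard. None of those provisions, however, gives an agreed count after patient 10.

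The gain is also modest and depends on assumed rates. With ≥6/20 added, a 22% rate still escapes 56% of the time (1 − 0.443) and a 30% rate 28% (1 − 0.719). At 17%, extra pauses may be a cost, since section 15.4 describes the combination's safety profile as manageable. This stands too.

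Finally, the proposal extends one rule of four, in a trial whose main concern is graft rejection. That is a fair limit on its reach. Discontinuation is the rule with a directly matching benchmark in section 14.2, and reasons and dates are already recorded. That makes it easy to extend, but does not show that discretion is enough for the other three.

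**Conclusion.** The point holds as an optional, low-cost improvement. Sections 10.4 and 14.2 agree with each other and contain no error, but their discontinuation limit stops at patient 10 of 30. A second limit at 6 of 20 adds 0.5 points of unnecessary pauses at the 11% benchmark and gains 6.0 points at 22% and 10.1 at 30%. At 30% it recovers about a quarter of the misses (10.1 of 38.3 points). The most discontinuations possible without meeting a written limit fall from 22 to 15 of 30 (5 of the first 20 plus all of the last 10).

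The table assumes independent patients and a constant rate. The arithmetic is firm; the need for the change is a judgement, because the plan does not say what rate would be unacceptable.

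**What to change.** In sections 10.4 and 14.2, keep the limit at 10 patients and add one cumulative trigger: pause and review if 6 or more of the first 20 patients discontinue immunotherapy for treatment-related adverse events. This keeps the existing 30% proportion (3/10 = 6/20). Count events as they are recorded, name the data safety monitoring board in both sections as the synopsis does, and state that the trigger leads to a review rather than a binding stop. If a tighter screen is wanted, use 5 of 20 and accept 2.7 points more pauses at 11% and 9.5 at 17%.

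The cost is protocol wording and one tabulation of data already in REDCap, with no added patients or staff. A halt of 1 to 3 months (assumed) would delay 0.625 × 1 to 0.625 × 3, about 0.6 to 1.9 enrolments, and transplant candidates could not enter meanwhile. Weighted by the added chance of a pause at 11%, the expected delay is 0.0049 × 1 to 3 = 0.005 to 0.015 months for 6 of 20, and 0.0266 × 1 to 3 = 0.03 to 0.08 months for 5 of 20. At 17%, 6 of 20 gives 0.0275 × 1 to 3 = 0.03 to 0.08 months.

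Deaths, locoregional-therapy events and failure to reach transplant after patient 10, and all events in patients 21 to 30, would still rest on discretionary review.
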